**Exit criteria:**

- a. Subjective withdrawal: the patient explicitly refuses to continue to participate in the study or adopts the anastomosis method of reconstructing the ileocecal valve.
- b. Withdrawal by the investigator:
  - During or after the operation, complicated conditions (such as severe abdominal adhesion, more difficult than expected) are found, which make it impossible to complete the operation according to the established plan.
  - The patient's postoperative condition changes (such as severe complications, infection, etc.) are not suitable for continued participation in the study after evaluation by the investigator.
- c. Missing follow-up: the patient is unable to complete the follow-up (e.g., lost

contact, refusal to further examination).

d. Protocol deviation: the subject did not receive the intervention or follow-up as required by the study protocol, affecting the validity of the data.

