Figure 2 Schematic of RISE anastomosis steps. A-B: Identify and mark the transection sites on the transverse colon stump and terminal ileum. C-D: Evert the terminal ileum to mimic the anatomical structure of the ileocecal valve. E-F: Place fixation sutures at the transverse colon opening. G-H: Complete the RISE anastomosis of the terminal ileum with colon.

b. Conventional lateral side anastomosis group (control group)

After inserting the same cannula, ligating blood vessels, and making a 10 cm distal transection at the transverse colon mass along with a 15 cm proximal transection at the ileocecal valve, the specimen was extracted through a small midline incision. A linear stapler was used in vitro for the side-to-side ileocolonic anastomosis, followed by closure of the common intestinal incision with a second stapler. The anastomotic site was reinforced with 3-0 catgut sutures using reverse-staple technique.

(2) Intraoperative index recording:

- Total operation time (min);
- Surgical duration of anastomosis (min);
- Blood loss during operation (mL);
- Blood transfusion volume (mL);
- 

(3) Immediate postoperative monitoring:

- Blood pressure, heart rate, respiration and body temperature at 24h, 48h and 72h after surgery;
- Daily postoperative physical examination (abdominal signs, resumption of bowel sounds);
- Bristol stool score (recorded daily for 7 consecutive days);

(4) Laboratory test:

Blood routine and blood biochemistry (monitoring inflammatory indicators and metabolic status) at 24h and 72h after surgery;

(5) Postoperative complication records (according to Clavien-Dindo grading system):

Table 1. Clavien-Dindo grading system for surgical complications

I	
 
① Abnormal conditions that do not require medication or surgery, endoscopy and radiation therapy.
 
② Antispasmodic, antipyretic, analgesic, diuretic, electrolyte and other drug therapy and physical therapy.
 
③ Open infected wounds at the bedside
 

II	
 
① Complications requiring the use of medications other than those described above for treatment of grade I complications.
 
② Blood transfusion, total parenteral nutrition
 

III	Complications requiring surgery, endoscopy or radiation therapy
IIIa	No general anesthesia is required
IIIb	Need general anesthesia

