## **5. End-point indicators**

Key endpoint indicator: Time to first stool formation post-surgery (Bristol Stool Score <4): The Bristol Stool Scale categorizes stool into seven grades. As stool shape correlates with retention time in the colon, this score helps assess both intestinal transit time and anastomotic function. Scoring criteria: >5 indicates diarrhea, 6 represents mild diarrhea, and 7 signifies severe diarrhea. (Detailed scoring guidelines are provided in the appendix)

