### **6. Data management and statistical analysis**

The clinical departments utilize the institution's electronic medical record system to compile relevant patient data. Clinical outcomes are systematically analyzed by designated personnel using SPSS 22.0 statistical software. Categorical data are presented as [count (%)], analyzed through  $\chi^2$ -tests. Quantitative data, validated by S-W method testing for normal distribution, are expressed as  $(\bar{x} \pm s)$  and evaluated using t-tests. Statistical significance is defined as  $P < 0.05$ .

Follow-up processing: The lost cases were included in the intention-to-treat (ITT) analysis, and multiple interpolation was used to fill in the missing data.

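### Exit criteria b and d let patients leave after randomisation for outcome-related reasons, and the protocol does not say that their outcome data are still collected

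*Protocol*

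**What the plan says.** Consent is taken before surgery (Protocol III.1), and the allocation envelope is opened once consent is signed (III.1.1). Any exit during or after the operation therefore follows randomisation.

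The Exit criteria (III.2) include:

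- **b, first bullet:** withdrawal by the investigator where "complicated conditions (such as severe abdominal adhesion, more difficult than expected) are found, which make it impossible to complete the operation" as planned.
- **b, second bullet:** withdrawal of anyone whose "postoperative condition changes (such as severe complications, infection, etc.) are not suitable for continued participation in the study after evaluation by the investigator".
- **c:** a separate item, "Missing follow-up: the patient is unable to complete the follow-up".
- **d:** protocol deviation, where "the subject did not receive the intervention or follow-up as required by the study protocol, affecting the validity of the data".

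The one statement on intention to treat is in III.6: "The lost cases were included in the intention-to-treat (ITT) analysis, and multiple interpolation was used to fill in the missing data".

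The primary endpoint (III.5) is "Time to first stool formation post-surgery (Bristol Stool Score <4"). Its raw data come from postoperative monitoring in III.4: "Bristol stool score (recorded daily for 7 consecutive days"). Section III.1.2 names only patients as blinded.

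**The concern.** Criteria b and d describe events after allocation that plausibly go with slower or otherwise different bowel recovery. The arms differ in how the bowel is reconstructed, so such events may also be more common in one arm. The second bullet of b turns on the judgement of an investigator who is not stated to be blinded. Criterion d reaches patients who did not receive the assigned intervention, and an ITT analysis is meant to keep those patients.

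The protocol speaks of leaving the study. It does not distinguish stopping or departing from study procedures from ending the collection of outcomes. A centre could reasonably stop recording Bristol scores for a patient withdrawn in theatre or on the first days, and five centres could each do this differently. Later outcomes (nutrition, quality of life, recurrence) are exposed in the same way.

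This is not a complaint that analysis sets are undefined, since those may be in the SAP. What is at stake is data collection, which only the protocol governs.

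**Working it through.** **1. Side-by-side reading.** Exit reasons b, c and d are listed separately. The ITT sentence names lost cases. The nearest match is c, but the term may be a translation that means all dropouts. No sentence says that b or d exits are dropped, and none says that their scores continue to be collected. The text leaves both open.

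**2. Inputs for an illustration.** III.3 gives day-2 stool formation of 65% versus 33.3%, two-sided alpha 0.05, 85 per group and 10% dropout. The plan's inflation reproduces as written: 85 + 8.5 = 93.5, rounded to 94 per arm and 188 in total. The documents give no rate of b or d exits. I assume 10% (the whole all-cause allowance, 94 − 85 = 9 patients) or 5%, with exits dropped from the analysis.

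**3. Formulas.** Let p be the true day-2 rate, f the share leaving an arm, and r the formation rate in exits relative to the arm average (r = 0.5 for half rate, r = 0 for unformed).

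- Retained rate = p(1 − f·r)/(1 − f).
- Retained n = 94(1 − f).
- Type I error = 1 − Φ(1.96 − d/SE) + Φ(−1.96 − d/SE), where d is the difference in retained rates and SE is the pooled standard error.

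*Worked case: no true effect, p = 0.333 in both arms, 10% unformed exits in one arm only.*

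- Retained rates: 0.333/0.9 = 0.370 (n = 84.6) against 0.333 (n = 94).
- Pooled rate: 0.3505. SE = √[0.3505 × 0.6495 × (1/84.6 + 1/94)] = 0.0715.
- d/SE = 0.037/0.0715 = 0.5175.
- Type I error = 0.0746 + 0.0066 = 0.081.

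| Exits, one arm / other | Half rate (r = 0.5) | Unformed (r = 0) |
|---|---|---|
| 10% / 10% | 0.050 | 0.050 |
| 10% / 5% | 0.052 | 0.058 |
| 10% / 0% | 0.058 | 0.081 |

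If exits form stool at the average rate (r = 1), the error is 0.050 throughout.

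**4. Time to event.** The primary endpoint is a time, so the same question was simulated with a log-rank test over days 1 to 7. The protocol does not name that test, so this is an assumption. There were 60,000 trials per cell. In both arms 10% of patients are slow, and exits come from the slow patients. The columns give exits in one arm / the other.

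| Slow patients and handling | 10% / 10% | 10% / 5% | 10% / 0% |
|---|---|---|---|
| Half rate, dropped | 0.051 | 0.060 | 0.080 |
| Half rate, scores to day 3 kept, then censored | 0.051 | 0.051 | 0.057 |
| Outer bound: none formed by day 7, dropped | 0.052 | 0.095 | 0.212 |

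With all randomised patients kept, the error is 0.050 to 0.053 in every cell.

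**5. Estimate at the planned effect** (65 − 33.3 = 31.7 points), exits dropped:

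| Exits | Half rate | Unformed |
|---|---|---|
| 10% in both arms | 33.5 | 35.2 |
| 10% in RISE only | 35.3 | 38.9 |
| 10% in control only | 29.9 | 28.0 |

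**6. Power in the least favourable of these cases** (control only, unformed). With d = 0.280, pooled SE 0.0749 and unpooled SE 0.0719, power = Φ[(0.280 − 1.96 × 0.0749)/0.0719] = Φ(1.85), about 97%. With 94 per arm and no exits it is about 99%.

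**The case against.** The two sections do not contradict each other. III.6 invokes intention to treat with imputation, and ITT ordinarily means everyone randomised. Naming the lost cases need not exclude the rest. A reader might infer that the protocol removes b and d exits from the analysis; it does not say so, and this point does not rest on it. The SAP mentioned in Section V.7 may define the analysis sets.

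A reader might also infer that every severe complication or deviation leads to exit. Both criteria are conditional: on the investigator finding the patient unsuitable, and on the deviation affecting data validity.

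Exposure of the primary endpoint is limited. Scores run for seven days, and nothing in the exit criteria deletes those already recorded. A patient who leaves after day 2 has complete day-2 data, and keeping scores to day 3 brings the largest half-rate log-rank figure down from 0.080 to 0.057. Exits for an uncompleted operation come earlier, so this does not cover every case.

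The largest error rates also need stacked assumptions: the whole dropout allowance given to b and d exits, all in one arm, all slow or unformed, and all their data discarded without the imputation that III.6 specifies.

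These objections stand and narrow the point. They do not answer its core: the protocol does not say that collection continues, and imputing uncollected scores would rest on assumptions about patients who left because of difficult surgery or complications.

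**Conclusion.** The point holds in a limited form and should be fixed. As written, the protocol permits outcome-related, and possibly arm-related, loss of the daily Bristol scores and later outcomes, and it leaves unclear whether its ITT sentence covers these patients.

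The size cannot be known from the documents. Under the stated assumptions, the day-2 type I error is 5% when exits are equal, 5.2% to 5.8% with 10% versus 5%, and 5.8% to 8.1% in the extreme one-arm case. The planned difference of 31.7 points would be estimated at between 28.0 and 38.9. A changed conclusion at the planned effect is unlikely.

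Two stronger readings are not supported. One is that the trial is biased towards RISE: the documents give no exit rates by arm, and the illustration moves either way. The other is that complications go unrecorded: Section IV covers adverse events to 30 days, and the research process table lists complications at every postoperative visit to one year. My confidence is medium, because the meaning of *lost cases* is unsettled.

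**What to change.** - **III.2, Exit criteria b and d:** state that these are reasons to stop or depart from study procedures and do not end outcome collection. The daily Bristol score to day 7 and the later outcomes continue to be collected unless the patient withdraws consent. Clinical decisions stay with the investigator.
- **III.6, ITT sentence:** replace the reference to lost cases with all randomised patients, analysed as randomised. Use deviations only to define a per-protocol sensitivity analysis.

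**Cost:** protocol wording, and follow-up of up to about 9 more patients per arm at the planned dropout. The treatment estimate may move in either direction as a result.

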#### **Termination criteria:**

a. Study intervention-related risks: serious safety problems were found during the study (such as significantly higher incidence of serious complications such as anastomotic leakage and massive hemorrhage than expected), and the study was terminated after evaluation by the ethics committee.

b. Ineffective: The interim analysis showed that the intervention (RISE anastomosis) did not achieve the predefined superiority and efficacy goals, and continued study was clinically meaningless.

c. External request for termination:

The ethics committee or regulatory authorities require the termination of the study due to safety or ethical issues. The research funds or resources are insufficient to sustain the study.

d. Force Majeure: The research cannot be continued due to force majeure such as natural disaster or epidemic.

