## **III. RESEARCH DESIGN**

### **1. Research on the overall design**

This prospective, single-blind, double-arm, multicenter, randomized controlled clinical trial with superiority design aims to compare postoperative intestinal function recovery between complete laparoscopic/robot-assisted right hemicolectomy combined with RISE anastomosis and traditional side-to-side anastomosis in patients with right-sided colon cancer. Eligible participants will be randomly assigned into RISE anastomosis and conventional anastomosis groups through zonal randomization, with evaluation of key outcomes including postoperative bowel function recovery (primary endpoint), complications, nutritional metabolism, quality of life, and oncological prognosis. Patients must provide informed consent prior to surgery, and all procedures are performed by senior physicians with extensive experience at each

center to ensure standardized protocols.

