### **3. Sample size:**

This prospective, double-arm, single-blind, multicenter randomized controlled trial evaluated the effectiveness of RISE anastomosis with ileocecal valve reconstruction. The postoperative stool formation time served as the primary endpoint for sample size calculation. Based on our prior trial results, the stool formation rate was approximately 65% in the RISE group and 33.3% in the control group on day 2 postoperatively. With a two-tailed test level  $\alpha=0.05$  and a 1:1 group ratio, PASS11.0 software estimated minimum sample sizes of 85 cases per group. Considering a 10% dropout rate, each group required 94 additional cases ( $85 + 85 \times 10\%$ ), totaling 188 cases combined. The study employed block randomization with minimum blocks of 4 samples. Subsequently, sample allocation was determined based on regional average patient intake levels to match block sizes.

According to the number of patients with right-sided colon cancer admitted by each center per year, the number of cases was allocated proportionally among the research centers,

Table 1 Sample size allocation of each sub-center

Center units	Sample size allocation
Second Affiliated Hospital of Army Military Medical University	108
The First Affiliated Hospital of Chongqing Medical University	20
Affiliated Hospital of North Sichuan Medical College	20
Guangan People's Hospital, Sichuan Province	20
Third People's Hospital of Yibin City, Sichuan Province	20

[figure not shown]

Figure 1 PASS11.0 software interface-sample size calculation results

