## **6. Communication and coordination mechanisms**

Regular meetings: kick-off meeting, mid-term analysis meeting and summary meeting to ensure that all centers update progress and problems simultaneously; establish a steering committee to resolve disputes.

Problem feedback and correction: set up a central mailbox or online platform to report problems (such as plan deviation, equipment failure) in real time; formulate the "plan deviation processing process" to record and analyze the root cause.

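### Termination criterion b permits stopping for ineffectiveness on missed interim superiority, which is not evidence of futility; its second condition has no criterion

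*Protocol*

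**What the plan says.** The trial is described in section III.1 of the protocol as a "multicenter, randomized controlled clinical trial with superiority design". Under Termination criteria in section III.2, item b covers ineffectiveness: "The interim analysis showed that the intervention (RISE anastomosis) did not achieve the predefined superiority and efficacy goals, and continued study was clinically meaningless". It has two parts. The first, on the superiority and efficacy goals, is statistical. The second, joined to the first, is a judgement: "and continued study was clinically meaningless". The protocol gives no measure for the second part.

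Section III.3 sizes the trial as a single two-sided comparison at the 0.05 level with 1:1 allocation. Its planning assumption is that "the stool formation rate was approximately 65% in the RISE group and 33.3% in the control group on day 2 postoperatively", and from this "PASS11.0 software estimated minimum sample sizes of 85 cases per group". It mentions no interim look. Section III.6 has one significance rule ("Statistical significance is defined as" P < 0.05). The only other reference to a mid-trial analysis is in section V.6, which lists a "kick-off meeting, mid-term analysis meeting and summary meeting" among the means of communication between centers; it sets no efficacy look. Section V.7 refers to a SAP, and names it for center effects.

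**The concern.** A futility rule should ask whether the final analysis can still succeed. Item b asks whether superiority has already been shown. These are different questions. At an interim look much of the information that gives the trial its power has not been collected, so an effective treatment with a good trend will often not yet be significant. A committee told that superiority was missed would have met the only statistical condition in the rule, and would have nothing in the protocol to tell it when continuing is pointless.

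At stake is the false-negative risk: a useful anastomosis technique could be abandoned as ineffective on data that do not show it. The planning rates come from the team's own earlier results, which the Research Context describes as preliminary and small-sample. A true effect smaller than planned is therefore plausible, and it would make a missed interim goal more likely.

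**Working it through.** **Inputs from the protocol (section III.3).** Rates 65% and 33.3% on day 2; two-sided alpha 0.05; 1:1 allocation; 85 per arm before dropout.

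**Assumptions, because the protocol gives no figure.** One interim look, at 42 per arm (about half of 85) or 28 per arm (about one third). The interim goal is two-sided P<0.05 in favor of RISE on the day-2 proportion. The trial stops whenever the goal is missed, so the second condition is ignored.

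**Step 1: the plan's own figure.** Power for two proportions with a pooled test is Φ[(p1 − p2 − 1.96·s0)/s1], where s0 = √(2·p̄(1 − p̄)/n), s1 = √(p1(1 − p1)/n + p2(1 − p2)/n) and p̄ = 0.4915.

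- At n = 85: s0 = 0.0767, s1 = 0.0727, and (0.317 − 1.96 × 0.0767)/0.0727 = 2.29, so power is 98.9%.
- The readable text states no target power, so 85 cannot be derived from the stated inputs alone. The same formula gives 38 per arm for 80% power, 51 for 90% and 87 for 99%; 85 is therefore consistent with a target near 99%.
- Dropout: 85 × 1.1 = 93.5, rounded up to 94; 2 × 94 = 188, as stated.

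**Step 2: how often the planned effect misses superiority at the look.**

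- n = 42: (0.317 − 1.96 × 0.1091)/0.1035 = 1.00, so the power at the look is 84.1% and the miss rate 15.9%. Exact binomial calculation gives a miss rate of 13.4%.
- n = 28: (0.317 − 1.96 × 0.1336)/0.1267 = 0.435, so the power at the look is 66.8% and the miss rate 33.2%. Exact: 34.2%.

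**Step 3: what would have happened to the stopped trials.** Exact binomial probabilities for a look at n and a final test at 85 per arm, with rates 65% and 33.3%:

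| Look (per arm) | Miss goal at look | Miss, but would win at 85 | Share of misses | Power with the stop |
|---|---|---|---|---|
| 42 | 13.4% | 12.6% | 93% | 98.9% − 12.6% ≈ 86.4% |
| 28 | 34.2% | 33.2% | 97% | 98.9% − 33.2% ≈ 65.7% |

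**Step 4: sensitivity.**

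- If the true rates were 55% and 33.3% (an assumption, not a protocol figure), a look at 42 per arm would miss the goal in 44% of trials and power would fall from 83% to 54%.
- If the interim goal were an O'Brien-Fleming-type bound instead of P<0.05, about 51% of trials at the planning rates would miss it at half-way. A stricter goal makes this trigger worse.

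**Step 5: a rule that does ask about futility.** Conditional power for the final test under the current trend is Φ[(Z/√t − 1.96)/√(1 − t)], where Z is the interim statistic and t = 42/85. It falls below 10% when Z is below about 0.74, whereas the P<0.05 goal is missed whenever Z is below 1.96.

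| Rule at 42 per arm | Stops at 65% vs 33.3% | Power | Stops with no effect |
|---|---|---|---|
| Superiority missed (P<0.05) | 13.4% | 86.4% | about 97% |
| Conditional power < 10% | 1.3% | 98.0% | about 78% |

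**The case against.** The strongest reply is that item b has two conditions. A promising but not yet significant trend would hardly be judged not worth continuing, so the calculations model a harsher rule than the one written. This stands. A reader might infer that the trial ends automatically when the interim is not significant, and the text does not support that. It does not remove the point, because an undefined judgement does not turn missed superiority into a test of futility.

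Second, interim timing, thresholds and whether a rule is binding are commonly left to a SAP, and the reference to predefined goals suggests that they are set elsewhere. This also stands: their absence here is no finding, and the timing, the P<0.05 goal and the use of the day-2 proportion are assumptions. Section III.5 defines the primary endpoint as a time to event; the proportion is used because section III.3 sizes the trial on it. What the protocol itself fixes is the quantity, superiority reached or not. A futility boundary in the SAP would measure something other than what item b describes.

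Third, a reader might infer that the look inflates the type I error. The documents do not support that. None of the listed termination grounds is success, no passage permits an efficacy claim at the interim, and a stop for futility alone does not raise the false-positive rate. The single P<0.05 rule is no defect on this account.

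Fourth, a reader might infer that the sample size cannot carry a look. At the planning rates power stays above 80% with the look at half-way even under the harsh reading, and no target power is stated in the readable text. A shortfall therefore cannot be shown there. Larger losses need an earlier look, a smaller effect or a stricter goal, none of which the protocol states.

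**Conclusion.** The point holds in a limited form. Item b permits, but does not compel, ending the trial as ineffective when superiority has been missed at an interim. That is the wrong statistical quantity for futility, and the accompanying judgement has no criterion.

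If every miss led to a stop, a half-way look at P<0.05 would stop about 13% of trials with the planned effect, most of them future successes, and reduce power from 98.9% to about 86%. A look at one third would stop about 34% and leave about 66%. For a given look and goal these are upper bounds on the harm, because the second condition may prevent some stops. The true size depends on timing and thresholds that the SAP may set. The consequence is a possible loss of power only. This is a cheap improvement, not a demonstrated failure of the design.

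**What to change.** Reword item b as a non-binding futility criterion based on the chance of success at the final analysis. For example: at a stated information fraction, stopping for futility may be considered if conditional power for the final primary test is below a stated bound such as 10%. The information fraction, the bound and the assumed trend are the sponsor's choice, and the figures can sit in the SAP with a cross-reference. State that no efficacy claim is made at the interim. Add one line to section III.3 giving the effect of the look on power.

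The cost is protocol wording and one pre-specified calculation, with no extra patients. The downside is that fewer truly ineffective trials would stop early: about 78% instead of about 97% in the half-way illustration.
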